5.3 Interruption or Discontinuation of Treatment

5.3.1 Discontinuation of study drugs

See section [4.4.1](#)

5.3.2 Interruption of study drugs

No study drug interruption is allowed unless for safety reasons.

5.4 Study Discontinuation

See section [4.5](#)

6 Treatment of Subjects

6.1 Treatment regimen

Patients will receive study drug: empagliflozin or placebo for an exposure period of up to 16 weeks - at the two treatment periods in a crossover design. Dosage, dosage regimen and route of administration are detailed in [4.3.1](#)

6.1.1 Treatment assignment

This study will be double blind. At the Baseline/randomization visit, qualified patients will be randomly assigned in a 1:1 ratio to either empagliflozin at a dose of 10 mg/day or placebo (study drug packages will be identical for all treatments).

Each patient's treatment will be assigned manually on the basis of a pre-determined randomization schedule prepared by the data management of the study CRO (_____). The randomization code will be generated and stored under secure and blinded conditions. The randomization will include stratification logarithm by ischemic versus non-ischemic cardiomyopathy and PVC burden at screening of $<$ or \geq to 4%

Each subject will be assigned a subject screening number.

The screening number will be structured so that each subject participating in the study will have a unique number. Screening number must not be re-used for different subjects. In case a subject is re-screened, the initial screening number should be retained and used.

Once subject's eligibility is confirmed, a subject will be assigned with a unique randomization number and will be randomized to treatment arm according to the randomization list Randomization number which will start with an RND or ENR followed by the site number and 3 digit subject number (for example – RND/ENR01-001, RND/ENR01-002 etc. for site number 1, etc.)

A dedicated "Subject Identification Log" will be kept at site. This log will include the subject's identifying details (e.g. name, ID number, telephone number) together with the screening and randomization number (if applicable).

The "Subject Identification Log" will be kept only at the investigational site and will not be taken out of the site.

6.2 Concomitant therapy

In general, concomitant medications and therapies deemed necessary for the supportive care and safety of the patient are allowed, provided their use is documented in the patient records and on the appropriate Case Report Form. The administration of antiarrhythmic treatment other than beta blockers

is NOT permitted. Similarly, the use of other concurrent investigational drugs is not allowed. The use of any of the prohibited medications or drugs/illegal substances within the prohibited time period will be considered a protocol deviation, which must be recorded on the appropriate CRF(s) or deviation violation form. Subjects with repeated protocol deviations may be discontinued from the study at the discretion of the investigator and/or sponsor.

6.3 Treatment compliance

Number of study drug tablets administered orally to every subject at home, will be evaluated by blister check up by the study coordinator/investigator and accounted on CRF.

7 Assessment of Efficacy

Efficacy assessments will be evaluated by: PVCs burden, NSVT number, Composite endpoint of: number of sustained VT+VF, ATP or delivery of shock therapy, BNP, End diastolic diameter and ejection fraction.

7.1 PVCs Burden

The primary efficacy parameter to be assessed will be PVCs burden.

PVCs burden is defined as the PVCs percentage of all beats in a pre-specified period captured on ICD or CRTD/P device.

PVCs burden will be evaluated as a part of the device interrogation on visit 1 to assess device integrity and proper function, in visit 2 to assess patient's eligibility for the study according to in- and exclusion criteria. In visits 3 and 5 to assess for treatment efficacy.

Assessment of the PVCs will be based on PVC counters for the various ICD/CRTD/P interrogated (from Medtronic, St. Jude, Guidant – Boston Scientific, Biotronik). Monitor counter reset will be conducted on visit 1,2,3,4 and 5. The equation for calculating the PVC burden for monitoring providing the PVC number per period will be:

$$PVC\ Burden(\%) = \frac{Number\ of\ PVCs}{Average\ HR\ \left(\frac{beats}{minute}\right) * 60 * 24 * (\#days\ in\ the\ period\ assessed)}$$

For monitors providing the PVC burden per hour the calculation will be:

$$PVC\ Burden(\%) = \frac{Average\ \frac{PVC}{hour}}{Average\ Heart\ Rate\left(\frac{Beats}{Minute}\right) * 60}$$

In case of device malfunction, counter malfunction or any other cause of inability to readout the device PVC counter measurement, PVC burden will be

calculated from a 12 Lead ECG Holter for 24 hours conducted at one of the last 7 days of the period assessed and will be calculated as:

$$PVC\ Burden(\%) = \frac{Number\ of\ PVCs}{Average\ Heart\ Rate\ \left(\frac{beats}{minute}\right) * 60 * 24}$$

Monitor counter readout and resetting will be performed by an electrophysiologist technician; data will be entered into the CRF by the study coordinator after approval of the principal investigator.

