4.1 Primary and secondary endpoints

4.1.1 Primary Endpoint

The primary endpoint is the burden of premature ventricular complexes, defined as the PVCs percentage of all beats in a pre-specified period captured on ICD or CRTD/P device.

PVC burden will be calculated according to device interrogation. In case of device failure to appropriately monitor the PVC burden, 24hr 12 lead holter ECG recording will be used as a complimentary method for arrhythmia assessment.

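### The Holter fallback formula for PVC burden divides by a fixed 24 hours and so understates the primary endpoint when fewer hours are analysable; the count formula leaves its day count undefined, and all three formulas omit x100

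*Combined protocol and SAP*

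**What the plan says.** Section 4.1.1 makes PVC burden the primary endpoint, "defined as the PVCs percentage of all beats in a pre-specified period captured on ICD or CRTD/P device". Section 7.1 repeats that definition and gives three formulas, each labelled as a percentage:

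1. Count-based devices ("The equation for calculating the PVC burden for monitoring providing the PVC number per period will be"): number of PVCs / (average heart rate x 60 x 24 x days in the period).
2. Hourly-rate devices ("For monitors providing the PVC burden per hour the calculation will be"): average PVCs per hour / (average heart rate x 60).
3. Holter fallback, for a device or counter that cannot be read: number of PVCs / (average heart rate x 60 x 24). The burden is "calculated from a 12 Lead ECG Holter for 24 hours conducted at one of the last 7 days of the period assessed".

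On the counters, section 7.1 says: "Monitor counter reset will be conducted on visit 1,2,3,4 and 5". Section 4.2.2 allows 7 days either side at visits 2 to 5. Burden is also used on a percent scale elsewhere: 2% is one route to eligibility in section 5.1, and 4% is the stratification cut-off in sections 4.2 and 6.1.1.

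The plan has no rule for a Holter with fewer than 24 analysable hours. It does not say whether the days in formula 1 are scheduled or actual, and it does not ask for the date and time of each counter reset.

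**The concern.** A percentage of captured beats needs a numerator and a denominator that cover the same recording time. Formula 3 breaks this. Hours lost from the recording contribute no PVCs to the numerator, but their beats stay in the denominator. Formula 1 breaks it too if the days entered are not the days over which the counter ran.

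The primary analysis in section 9.2.1 compares a patient's two treatment periods. If both periods lose the same share of recording, both values shrink in proportion, and so does their difference. If the loss differs, or one period is read by device and the other by an incomplete Holter, part of the within-patient difference comes from the formula and not from treatment.

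The absent x100 is a separate matter of scale. A value computed literally cannot be set against the 2% and 4% cut-offs.

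**Working it through.** **Plan's own figures.** The documents contain no worked PVC burden to reproduce. The sample size does reproduce: with a difference of 10 and a standard deviation of differences of 40, a noncentral t calculation gives power 0.8015 at N = 128. It does not depend on these formulas.

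**Assumptions.** Average heart rate is 70 beats/min over the time actually recorded (it cancels in every ratio below). The recorded durations are illustrative, because the documents give none. True burden means PVCs over the beats actually recorded.

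**Formula 3, Holter, true burden 4%.** The denominator is fixed at 70 x 60 x 24 = 100,800 beats.

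| Analysed hours | Beats analysed | PVCs at 4% | Formula 3 (after x100) | Relative error |
|---|---|---|---|---|
| 24 | 100,800 | 4,032 | 4.00% | 0 |
| 22 | 92,400 | 3,696 | 3.67% | -8.3% |
| 20 | 84,000 | 3,360 | 3.33% | -16.7% |
| 18 | 75,600 | 3,024 | 3.00% | -25.0% |

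In general, reported burden = true burden x analysed hours/24. Dividing by analysed beats returns 4.00% in every row.

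**Mixed methods within a patient.** With no treatment effect and a true 4% in both periods, a device reading (4.00%) and a 20-hour Holter (3.33%) differ by 0.67 percentage points, or 16.7% in relative terms.

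**Formula 1, count-based device, true burden 4%.** The second treatment period runs from visit 4 (day 84 +/-7) to visit 5 (day 140 +/-7), so it can last 42 to 70 days. If a nominal 56 days is entered, the denominator is 70 x 1,440 x 56 = 5,644,800 beats:

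- 42 days counted: 0.04 x 70 x 1,440 x 42 = 169,344 PVCs; 169,344/5,644,800 = 3.0%.
- 49 days: 4 x 49/56 = 3.5%.
- 63 days: 4 x 63/56 = 4.5%.
- 70 days: 282,240/5,644,800 = 5.0%.

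The first period (visits 2 to 3) has the same range if both windows are used. It is 49 to 63 days if day 0 is fixed by randomisation. Entering the actual days since the reset gives 4.0% throughout.

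**Formula 2, hourly rate.** 168 PVCs per hour / (70 x 60) = 0.04. The result is the same for 24 or 20 recorded hours, provided the device averages over recorded hours.

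**Scale.** All three formulas return 0.04 for a 4% burden. The factor of 100 is constant and unrelated to how complete the recording is.

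**The case against.** The case for leaving section 7.1 alone has several good parts.

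- *The Holter is only a fallback, and formula 3 matches a full 24-hour test.* True. Section 5.1 requires a device able to record PVC burden, section 5.2 excludes ICD malfunction, and section 4.5 lists device malfunction among reasons for ending participation. That leaves mainly unreadable counters, and the recording must also be incomplete. This limits how often the error occurs but does not make the formula right.
- *The days in formula 1 can be read as actual days.* This stands as a fair reading, since counters are reset at every visit and sections 7.2 and 7.3 say the device is active throughout. On that reading formula 1 is correct. The text does not exclude the other reading.
- *A missing x100 is notation.* Largely true. A constant factor leaves the paired t, signed-rank and rank-sum tests unchanged, and it would be noticed against the 2% and 4% cut-offs. It matters only if some records are multiplied and others are not.
- *Blinding and randomisation turn unrelated losses into noise.* True for direction. Noise and proportional shrinkage remain.

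A reader might also infer more than the documents support:

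- That all three formulas divide by nominal time. Formula 2 does not, and for formula 1 it is only one reading.
- That the error is always downward. A nominal 56 days overstates burden when the counter ran longer.
- That counters cleared between visits lose data, chiefly in patients with VT or shocks. The documents schedule resets only at study visits. They do not say that an unscheduled interrogation clears the counter, and they draw no link to shocks.

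**Conclusion.** The point holds for the Holter formula as written: it gives a wrong value whenever fewer than 24 hours are analysable, by the factor analysed hours/24. For the count formula it is conditional on a nominal day count, and the error can then go either way. The hourly formula needs only the x100, and the x100 is a scale correction in all three.

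A reader might set the 16.7% or 25% against the planned effect of 10 in section 9.1 and conclude that the trial result is at risk. That comparison is not like for like: one figure is the error in a single patient-period, the other a mean over 128 patients. As an illustration, assume equal burdens and every affected recording on the same treatment, the worst case. If 5% of patients had a 20-hour Holter in one period only, the mean shift would be 0.05 x 16.7% = 0.8% in relative terms. With 10% of patients and 18 hours it would be 0.10 x 25% = 2.5%. The documents give neither frequency, so the effect on the trial result may be small.

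The correction is still worth making. It concerns the stated rule for the primary endpoint, the right rule follows from the plan's own definition, and the change costs almost nothing.

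**What to change.** In section 7.1:

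- Holter: burden (%) = 100 x PVCs / total analysed beats, or 100 x PVCs / (average heart rate x analysed minutes).
- Count-based devices: burden (%) = 100 x PVCs / (average heart rate over the same interval x actual minutes since the last counter reset). Record the date and time of each reset on the CRF.
- Hourly-rate devices: keep the formula and multiply by 100.

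Cost: a formula correction and one CRF field for the reset date and time. When the Holter is used, its analysed beats or minutes replace the assumed 24 hours in the calculation. No extra visit or procedure is needed, and the sample size is unaffected.

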7.2 Non-sustained ventricular tachycardia (NSVT)

Non-sustained ventricular tachycardia number is defined as the NSVT number in a pre-specified period captured on ICD or CRTD/P device interrogation, or as a backup information (in case of ICD or CRTD/P malfunction) on Holter ECG. The device will be activated during the whole study period and data will be captured on the CRF at visits 1 to 5. The Holter ECG device of 24 h' will be performed in case of device malfunction, counter malfunction or any other cause of inability to readout the device PVC counter measurement. Holter assessment will be conducted at one of the last 7 days of the period assessed. Data from study device/Holter will be captured on the CRF at visits 2, 3 and 5.

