
Assessments
 
Efficacy:
	
The following evaluations will be conducted to judge the efficacy of the treatment regimen:
 
Primary efficacy assessment is PVCs burden. PVCs burden will be evaluated as a part of the device interrogation on visit 1 to assess device integrity and proper function, in visit 2 to assess patient's eligibility for the study according to in- and exclusion criteria. In visit 3 and 5 to assess for treatment efficacy.
 
Assessment of the PVCs will be based on PVC counters for the various ICD/CRTD/P interrogated. Monitor counter reset will be conducted on visit 1,2,3,4 and 5. In the case of device malfunction, counter malfunction or any other cause of inability to readout the device PVC counter measurement, PVC burden will be calculated from a 12 Lead ECG Holter for 24 hours conducted at one of the last 7 days of the period assessed
 
Secondary efficacy assessments are:
 
NSVT rate: Non-sustained ventricular tachycardia rate is defined as the the number of NSVT events in a pre-specified period captured on ICD or CRTD/P device interrogation or as a backup information (in case of ICD or CRTD/P malfunction) on Holter ECG. The device will be activated along the whole study period and data will be captured on the CRF at visits 1 to 5.
 
Composite endpoint of: sustained VT+VF, ATP or delivery of shock therapy: All the four parameters will be captured on ICD or CRTD/P device interrogation. Data from study device will be captured on the CRF at visits 1 to 5.

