4.1.2 Secondary Endpoints

1. The number of non-sustained ventricular tachycardia (NSVT) episodes, defined as the NSVT number in a pre-specified period captured on ICD or CRTD/P device.
2. A composite cumulative endpoint of ventricular arrhythmia load (number of: sustained ventricular tachycardia, ventricular fibrillation, antitachycardia pacing (ATP) or delivery of shock therapy episodes, defined as the arrhythmias number in a pre-specified period captured on ICD or CRTD/P device.
3. The change in blood level of NT-Pro Brain Natriuretic peptide (BNP) from baseline to the end of any of the treatment periods
4. The change in Left ventricular end diastolic diameter on echocardiography from baseline to the end of any of the treatment periods.
5. The change in Left ventricular ejection fraction (EF) on echocardiography from baseline to the end of any of the treatment periods.
6. Safety.

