7.3 A composite cumulative endpoint of ventricular arrhythmia load

This is defined as the number of sustained ventricular tachycardia, and/or ventricular fibrillation, and/or tachycardia pacing (ATP) and/or delivery of shock therapy. All the four parameters will be captured on ICD or CRTD/P device interrogation. Sustained VT and NSVT will be captured as a backup information (in case of ICD or CRTD/P malfunction) on Holter ECG. The device will be activated during the whole study period. The Holter ECG device of 24 h' will be performed In the case of device malfunction, counter malfunction or any other cause of inability to readout the device PVC counter measurement. Holter

assessment will be conducted at one of the last 7 days of the period assessed. Data from study device/Holter will be captured on the CRF at visits 2, 3 and 5.

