9.2 Efficacy and Safety evaluation

General

All measured variables and derived parameters will be listed individually and, if appropriate, tabulated by descriptive statistics.

For categorical variables, summary tables will be provided giving sample size, absolute and relative frequency and 95% CI (Confidence Interval) for proportions by study treatment.

For continuous variables, summary tables will be provided giving sample size, arithmetic mean, standard deviation, median, minimum and maximum and 95% CI (Confidence Interval) for means of variables by study treatment.

All tests will be two-tailed, and a p value of 5% or less will be considered statistically significant.

The data will be analyzed using the SAS ® version 9.3 (SAS Institute, Cary North Carolina).

Analysis Populations

Safety Population: will include all randomized subjects who received any study drug.

Intention-to-Treat (ITT) Population: will include all subjects included in the safety population who provided at least one post-baseline assessment for the primary endpoint.

Per-Protocol Population: will include all subjects in the ITT population who complete the study in compliance with the protocol and have no major protocol violations.

9.2.1 Efficacy analysis:

The primary endpoint is the percentage of PVCs during the 2 months of empagliflozin treatment compared with the percentage of PVC on placebo.

The two-sample T-test or Non-parametric Wilcoxon-Mann-Whitney Rank sum test for independent samples (as is appropriate) will be applied for testing the carry-over effect in the primary endpoint between the two sequences.

If no carry-over effect will be observed, then The Paired T-test or non-parametric Signed-rank test for two means (as is appropriate) will be applied for analyzing the difference in the above changes between the tested treatment and placebo.

Otherwise, if a carry-over effect will be found statistically significant, then the MMRM model (Mixed-effect model for repeated measures) will be applied for analyzing the difference in the above reduction between the tested treatment and the placebo. The model will included terms for study arm (sequence), treatment and period as fixed effects, and subject nested within study arm as a random effect. Other covariates (such as age and baseline measures) will be included if they will be found different between the groups and affecting the outcome.

Secondary Endpoints:

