Frequency of non-sustained ventricular tachycardia (NSVT) episodes and composite cumulative ventricular arrhythmia load will be summarized by treatment.

Changes in blood level of NT-Pro Brain Natriuretic peptide (BNP), Left ventricular end diastolic diameter and Left ventricular ejection fraction (EF) from baseline will be summarized in appropriate tables by treatment.

9.2.2 Safety Analysis:

Data from all subjects who receive any study drug will be included in the safety analyses.

All adverse events will be coded using the Medical Dictionary for Regulatory Activities (MedDRA, most updated Version) terminology and presented in tables by System Organ Class (SOC) and Preferred Term (PT).

AE data will be listed individually and summarized by SOC and by PT within a system organ class under each treatment.

The severity of the toxicities will be graded according to the NCI CTCAE (Ver4.0) whenever possible. In the by-subject analysis, a subject having the same event more than once will be counted only once. Adverse events will be summarized by worst NCI CTC grade. Adverse events leading to death or to discontinuation from treatment, events classified as NCI CTCAE Grade 3 or Grade 4, study-drug-related events, and serious adverse events will be summarized separately.

Laboratory data will be graded according to NCI CTCAE severity grade.

Any deviations from the previously described statistical plan will be described and justified in a protocol amendment.

Other safety parameters including vital signs and physical examination will be summarized in appropriate tables.

Concomitant medications entered into the database will be coded using the World Health Organization (WHO) Drug Reference List, which employs the Anatomical Therapeutic Chemical classification system.

10 Direct Access to Source Data/Documents

Access to the subject's source data and study documents will occur only with the subject's acknowledgement and agreement by signing an informed consent. The investigator will permit study-related monitoring, audits, Institutional Review Board (IRB) review and regulatory inspection(s), providing direct access to source data and documents.

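### NSVT and the arrhythmia composite are counts with no monitored-time denominator, a 24-hour Holter may back up about 56 device days unscaled, and no within-patient estimate is clearly planned for the secondary endpoints

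*Combined protocol and SAP*

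**What the plan says.** **Definitions.** Section 7.2: "Non-sustained ventricular tachycardia number is defined as the NSVT number in a pre-specified period captured on ICD or CRTD/P device interrogation". The same sentence then allows a fallback source for that count: "or as a backup information (in case of ICD or CRTD/P malfunction) on Holter ECG". The synopsis uses the word rate, but what it defines is a number: "Non-sustained ventricular tachycardia rate is defined as the the number of NSVT events in a pre-specified period". Section 4.1.2 treats the composite of sustained VT, VF, ATP and shocks the same way: "defined as the arrhythmias number in a pre-specified period captured on ICD or CRTD/P device".

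**Holter backup.** Section 7.3, on the composite: "Sustained VT and NSVT will be captured as a backup information (in case of ICD or CRTD/P malfunction) on Holter ECG". Sections 7.2 and 7.3 specify a 24-hour recording on one of the last 7 days of the period and give no conversion to period length. Section 7.1 does handle this for PVC burden. Its device formulas divide by beats over the monitored time, and the Holter version, "calculated from a 12 Lead ECG Holter for 24 hours conducted at one of the last 7 days of the period assessed", has its own 24-hour denominator.

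**Analysis.** Section 9.2.1 on the two arrhythmia counts: "Frequency of non-sustained ventricular tachycardia (NSVT) episodes and composite cumulative ventricular arrhythmia load will be summarized by treatment". NT-proBNP, LVEDD and EF changes are likewise tabulated by treatment. The general text of section 9.2 adds, for continuous variables, "95% CI (Confidence Interval) for means of variables by study treatment". The carry-over test, paired test and mixed model in section 9.2.1 are written for the primary endpoint. Section 9.1 says the efficacy analysis uses the Wilcoxon signed-rank test.

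**The concern.** A raw count is comparable between two periods only if both were monitored for the same time by the same method. Neither is guaranteed here. A Holter-supplied count would look like near-complete suppression of NSVT in that patient's period, whichever treatment was being taken.

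The second issue is what will be reported. The crossover was chosen so that each patient serves as his or her own control. Separate summaries and CIs for each treatment carry the between-patient variance and do not give the treatment difference. The arrhythmia secondaries, and the cardiac-function objective in section 3.2 (NT-proBNP and echocardiography), would then have no clearly planned effect estimate. The estimator, the denominator and the handling of Holter data could all be chosen after the data are seen.

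**Working it through.** **The plan's own figure.** The only sample-size figure is 128, for PVC burden. With SD of differences 40 and difference 10 (section 9.1): N = (40 × (1.960 + 0.842) / 10)² = 125.6, so 126. The exact noncentral-t power at 128 is 80.1%. The figure reproduces, but no corresponding figure exists for NSVT or the composite.

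**Exposure in a substituted period.** Nominal period 56 days (8 weeks, section 4.2); Holter 1 day.
- Expected count relative to the device: 1/56 = 0.018, or 98.2% lower at an unchanged rate.
- Chance of a zero count at a constant Poisson rate: exp(−2/56) = 96.5% at 2 episodes per 56 days (the NSVT entry threshold in section 5.1 is 2 events in 2 months), and exp(−10/56) = 83.6% at an assumed 10.

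**Effect on the treatment comparison.** The documents give no substitution rate, so the shares below are assumptions. With no drug effect, and shares pE and pP of empagliflozin and placebo periods substituted, the ratio of mean counts is (1 − pE × 55/56) / (1 − pP × 55/56).
- Equal shares: 1.00.
- 3% versus 2%: 0.9705 / 0.9804 = 0.99.
- 4% versus 2%: 0.9607 / 0.9804 = 0.98.

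**Noise if substitution is random.** Simulation of 4,000 trials of 128 patients, true ratio 1. Assumed: gamma-distributed patient rates with mean 5 per 56 days and shape 0.5, within-patient log-SD 0.5, each period substituted independently. SD of the log rate ratio:

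| Periods substituted | Raw counts | Averaged daily rates | Offset model | Affected patients excluded |
|---|---|---|---|---|
| 0% | 0.127 | 0.127 | 0.127 | 0.127 |
| 2% | 0.133 | 0.142 | 0.130 | 0.130 |
| 5% | 0.139 | 0.154 | 0.132 | 0.133 |

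Relative to the offset model, raw counts cost (0.133/0.130)² = 1.05 in variance at 2% and (0.139/0.132)² = 1.11 at 5%. Averaging daily rates costs (0.154/0.132)² = 1.36 at 5%, because one Holter episode becomes 56 and a zero stays zero. The offset model avoids this: a 1-day/56-day pair has (56/57)/28 = 3.5% of the information of a 56/56 pair.

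**Device-only periods.** Counters run from reset to reset (section 7.1). Visits 4 and 5 are at day 84 ± 7 and day 140 ± 7 (section 4.2.2), so period 2 can last from 133 − 91 = 42 to 147 − 77 = 70 days, a ratio of 1.67. With no reason for visit timing to depend on blinded treatment, this is noise only.

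**Separate CIs versus a paired estimate.** If a reader judges the difference from two treatment-level CIs as if they were independent, its SE is overstated by 1/√(1 − ρ), where ρ is the within-patient correlation: 1.41 at ρ = 0.5 and 2.24 at ρ = 0.8 (both assumed).

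**The case against.** The strongest reply is that the effect on the result is small and the remedy partly a matter of taste. That stands in part. Section 5.2 excludes patients with evidence of ICD malfunction, section 5.1 requires a device able to record PVC burden, and section 4.5 lists device malfunction as a possible reason to discontinue. Substitution should therefore be rare. Excluding Holter-only periods also performs about as well as the offset model.

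Several stronger readings are tempting but unsupported:
- **That the plan builds in a 56-fold error or a bias towards the drug.** The formal definitions in section 4.1.2 are device-only, Holter is called backup, and no analysis text says a 24-hour count enters the summaries as a period count. The gap is a missing rule. Any bias needs substitution to differ by treatment.
- **That no test is planned for the secondaries.** The signed-rank sentence in section 9.1 could reach them, since section 7 lists them as efficacy assessments. But it sits in the primary-endpoint sample-size text, and even read broadly it gives no effect estimate or CI.
- **That early withdrawal truncates device counts.** Section 4.4.1 asks for a final evaluation without saying it includes interrogation, and section 4.5 says no follow-up will be recorded.
- **That the composite double-counts an arrhythmia and its therapy.** The rule is not spelled out, but section 4.1.2 counts episodes and section 7.3 joins the components with and/or, which can be read as one episode.
- **That a fault found at visit 3 or 5 is always found too late for Holter.** Table 2 schedules Holter at visits 2, 3 and 5; the problem arises only if Holter is reserved for malfunction.

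Descriptive secondary endpoints can be a legitimate choice. In a crossover, though, the description should still include the within-patient difference.

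**Conclusion.** The point holds as a gap in the secondary-endpoint plan that should be closed. NSVT and the composite lack a monitored-time denominator that the same document supplies for PVC burden, and an unscaled Holter count carries 1/56 of nominal exposure. The likely effect on the treatment comparison is modest: none on average if substitution is balanced, 1% to 2% in the assumed imbalances, and a variance cost of about 5% to 11% at assumed substitution rates of 2% to 5%. The missing within-patient estimate is the more consequential part, because it concerns every secondary efficacy endpoint however often Holter is used.

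The text findings are firm. The magnitudes rest on a constant Poisson rate, assumed substitution shares and assumed rate heterogeneity. The primary endpoint is not affected.

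**What to change.** 1. **Counts.** Analyse NSVT, and the composite where it is not too sparse, with a count model: log monitored time between counter resets (or Holter hours) as offset, treatment and period terms, and within-patient correlation. State in advance whether Holter-only periods are excluded from the main analysis or kept and down-weighted by the offset; run the other as a sensitivity analysis. Do not average simple daily rates across sources. Treat Holter-only periods as incomplete for the composite, since Holter is named as backup for only one of its components, sustained VT.
2. **Estimates.** For each secondary efficacy endpoint report a within-patient treatment estimate with 95% CI: a rate ratio for the counts, and a paired or crossover difference for NT-proBNP, LVEDD and EF. Label these as secondary, without multiplicity control, and state whether the signed-rank sentence in section 9.1 covers them.
3. **Reconcile.** Device malfunction is both a possible discontinuation reason (section 4.5) and the trigger for Holter backup (sections 7.1 to 7.3). Holter appears routine in Table 2 and the visit lists of section 4.2.2, but malfunction-only in the treatment-period text of section 4.2 and in section 7.2. These passages must be brought into agreement.

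The cost is SAP wording and one standard model. Monitored days follow from the resets already planned, and no visits are added. The downsides are an assumed constant rate within a period and possible sparsity of the composite, for which a simple rate ratio with a wide CI should be reported.
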